The hypothesis of this study is that in a population with a demonstrated perfusion defect and WMA (measured by Rb-82 PET), regadenoson stimulates changes in ventricular mechanics (radial strain and rotational displacement) and LVEF associated with the degree of ischemic or fibrotic burden. Additionally, these changes may be different for normal, ischemic, and infarcted myocardium and will be compared between a high-risk population and a cohort of low-likelihood normals.

PRIMARY END-POINTS

For each patient group, every segment of the myocardium will be classified as normal, reversible, or non-reversible based on the PET perfusion data. Then for each segment category the radial strain (ΔR) and rotational displacement ($\Delta\theta$) will be calculated using an industry

standard CMR software package (current plans are to use HARP®, Diagnosoft, Morrisville, NC, though another package may be used). These values will be determined from tagged cine images obtained in three short axis (apical, mid, and basal) views of the left ventricle obtained during regadenoson induced stress and at rest (or difference in stress values).

1. Primary End-Point 1 of this study is to determine if there is a measurable difference in the strain (ΔR) and/or displacement ($\Delta\theta$) of normal and abnormal segments between the defined ischemic and normal patient groups.
2. Primary End-Point 2 of this study is to determine if there are measurable differences in the strain (ΔR) and/or displacement ($\Delta\theta$) between segment classifications (normal, reversible, and non-reversible perfusion defects).

SECONDARY END-POINTS

Secondary end-points will be determined from tagged cine images obtained in three short axes (apical, mid, and basal) views of the left ventricle obtained during regadenoson induced stress and at rest (or difference in stress values).

1. Secondary End-Point 1 of this study is to determine the strain (ΔR) and/or displacement ($\Delta\theta$) scores correlate with flow reserve as measured by PET and/or transmural extent of infarction (TEI) indicated by Late Gadolinium Enhancement (LGE).
2. Secondary End-Point 2 of this study is to track any adverse events as a result of participation in this study.

STUDY DESIGN

Subjects who have had a clinically indicated, ECG-gated, Rb-82 myocardial perfusion PET study will be recruited for participation. Specific inclusion/exclusion criteria are:

Inclusion Criteria

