1. Myocardial rest/regadenoson stress perfusion PET study within 60 days
2. Rest LVEF (greater than or equal to 35%)
3. No change in symptoms or treatment between the PET and the MRI study
4. Willing to consent to the study
5. Male or female who is either post-menopausal, surgically sterile, or if has a childbearing potential, a negative pregnancy test within 2 days prior to the MRI study.
6. An estimated glomerular filtration rate completed within 6 months of participation.

Exclusion Criteria

1. Metallic implants, pacemaker, blood vessel clip (contra-indicated for MRI)
2. Patient size exceeds MRI bore/table limits: (Max body diameter > 70 cm, weight > 136 kg)
3. Second or third degree AV block
4. Sinus node dysfunction
5. Acute myocardial infarction (past 3 months)

6. Actively wheezing or with acute asthma or bronchospastic attacks requiring changes in therapy within the past 30 days
7. Patients that have experienced a previous hypersensitivity reaction thought to be related to regadenoson
8. Pregnant Women

STUDY PROCEDURES

Study staff will provide each subject with full and adequate verbal and written information using an IRB approved informed consent document, including the objective and procedures of the study and the possible risks involved before inclusion in the study. Informed consent will be obtained prior to performing any study-related procedures. If consent is gained, a copy of the executed consent form will be provided to the subject.

Following consent execution and prior to the MRI, the following screening measures will be performed and documented:

- Medical history, including surgeries and procedures;
- Medications, including herbal supplements and vitamins, will be reviewed;
- A MRI Patient Safety Screening questionnaire completed;
- Vital signs will be taken, to include heart rate, breathing rate, and blood pressure will be collected;
- An electrocardiogram will be performed;
- An intravenous catheter will be placed into the subject's arm;
- Females of child-bearing potential* will undergo a serum pregnancy test;
- If a creatinine blood test has not been done clinically in the last six months, one will be performed; and
- The qualifying, clinically-indicated cardiac PET procedure records will be collected.

** Females of childbearing potential are defined as not postmenopausal or surgically sterilized.*

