Consented subjects will be asked to undergo a rest/Lexiscan® (Regadenoson) stress cardiac MRI examination. For patients who do not have an estimated glomerular filtration rate on record within 6 months of participation, a creatinine will be drawn as part of the screening procedures. Patients with renal dysfunction (defined as an estimated glomerular filtration rate (GFR) < 60 mL/min/1.73m² within 6 months of participation) or a history of gadolinium contrast allergy or intolerance will participate in an abridged non-contrast protocol consisting of the localizer, functional and stress imaging sequences only, and no contrast will be administered.

There will be 40 subjects recruited into this study. 15 subjects will be recruited who had normal perfusion, normal LVEF and no WMA on a clinically indicated cardiac PET study. 25 subjects will be recruited into the ischemic cohort. Consented study participants will receive one dose of Lexiscan® (Regadenoson) while taking part in this protocol.

Ischemic Patient Population

The abnormal population will be selected from a group of patients with a clinically indicated myocardial perfusion PET study demonstrating reversible ischemic perfusion defect, a rest LVEF of $\geq 35\%$, and demonstrated WMA by quantitation, utilizing QPET's QGS analysis program

(Cedars Sinai Health System, Los Angeles, CA). A WMA will be defined as having a drop in LVEF from rest to stress and/or an extent of greater than or equal to 10% thickening and/or motion.

Myocardial perfusion rest/Regadenoson PET protocol

All PET studies will have been clinically indicated and performed prior to study participation. These studies will have been performed on a Biograph™-16 or Biograph™-64 PET/CT or Siemens ACCEL Dedicated PET system (Siemens Medical Solutions, Erlangen, Germany).

Biograph™-16 or Biograph™-64 PET/CT System

A low-dose CT image acquisition will have been acquired for attenuation correction. The resting perfusion images will have been acquired using 20-40 mCi of Rubidium-82, infused over 35 seconds. The ECG gated, list mode acquisition will have started prior to the start of the rubidium-82 infusion and continued for 7 minutes.

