Volumetric data and late gadolinium enhancement post-processing will be performed on an AW workstation using ReportCard v4 software (General Electric). Tagged images will be post-processed for strain and displacement (ΔR and $\Delta\theta$) measurements using the HARP® tagging analysis software package (Diagnosoft) or a similar industry standard software package.

Primary End-Point Analysis:

For each patient group, every segment of the myocardium will be classified as normal, reversible, or non-reversible based on the PET perfusion data. Then for each segment category the radial strain (ΔR) and rotational displacement ($\Delta\theta$) will be calculated using the HARP® software package (Diagnosoft). These values will be determined from tagged cine images obtained in three short axis (apical, mid, and basal) views of the left ventricle obtained during regadenoson induced stress and rest (or difference in stress values). Comparisons will be made using ANOVA and standard t-test methods.

1. For Primary End-Point 1 we will compare the radial strain (ΔR) and rotational displacement ($\Delta\theta$) of normal and abnormal segments *between the defined ischemic and normal patient groups*.
2. For Primary End-Point 2 we will compare radial strain (ΔR) and rotational displacement ($\Delta\theta$) at rest and stress *between abnormal and normal segment classifications*.

Secondary End-Point 1

The secondary end-points of this study will be analyzed using regression analysis to determine the relationships between radial strain (ΔR), rotational displacement ($\Delta\theta$), regional flow reserve, and the degree of transmurality (TEI) as defined by the presence of delayed gadolinium enhancement.

Secondary End-Point 2

Adverse events will be recorded on an Adverse Event log. This log will track:

1. Description of event
2. Start and stop time of event
3. Severity of event
4. Likelihood that the event is related to the study drug
5. Relationship of event to other test procedures
6. Any treatment actions taken
7. The final outcome

Although serious adverse events are not expected, serious adverse events will be reported to the IRB.

Powering Calculation

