The patient to patient variability of normal resting LVEF is 5.3% (3). For the normal patients, there is an expected increase in ejection fraction of 8% (3). For ischemic patients, we have defined a change in ejection fraction of 2% as being significant. The net change would be a 10% change in difference in ejection fraction between the control (normal) and the ischemic groups.

If we assume cylindrical geometry, this would imply a roughly 5.6% change in the radius of the myocardium would result in a change in ejection fraction of 10% (assuming a resting LVEF of 55). Based on (3), this would give a Cohen's d of 1.06 and a total of 16 patients per group. However, given the need to explore the abnormal arm of the study, can obtain a similar power of 0.8 using an unequal population sizes of 13 (normal) and 22 (abnormal). We anticipate approximately 15% of patients that may not achieve sufficient quality of data would yield population of 15 normal subjects and 25 ischemic subjects to achieve the 0.8 power.

RESEARCH ENVIRONMENT

ASPIRE Foundation

Study funding will be provided by Astellas to the sponsor, the ASPIRE Foundation. The ASPIRE Foundation is a not-for-profit, non-invasive, imaging-based foundation dedicated to furthering knowledge about the role of imaging in improving patient outcomes. The ASPIRE Foundation is a joint venture between Saint Luke's Cardiovascular Consultants, the Mid America Heart Institute, and Cardiovascular Imaging Technologies. The ASPIRE Foundation will subcontract with Cardiovascular Imaging Technologies for staff to conduct its trials. Only CVIT study-

specific staff (Co-PIs: Drs. [name] and [name]; Sub-PIs: Drs. [name] and [name]; and Study Coordinators: [name] and [name]) will have access to patient data.

Saint-Luke's Cardiovascular Consultants

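### Nothing in the plan keeps the tagging reader unaware of PET class and cohort, or sets a rule for rejecting poor data, so label-dependent processing is an unguarded risk to both primary end-points

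*Combined protocol and SAP*

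**What the plan says.** The PRIMARY END-POINTS section and the Primary End-Point Analysis (under DATA ANALYSIS) give the same sequence. First, "every segment of the myocardium will be classified as normal, reversible, or non-reversible based on the PET perfusion data". The next sentence starts "Then for each segment category the radial strain" and has radial strain and rotational displacement calculated with the tagging software.

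Other places bear on what the reader may know and what may be dropped:

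- **PET comes first.** The PET protocol section says "All PET studies will have been clinically indicated and performed prior to study participation", and cohort is defined from that PET study. Among the screening steps before the MRI, STUDY PROCEDURES lists: "The qualifying, clinically-indicated cardiac PET procedure records will be collected".
- **Who handles the data.** The ASPIRE Foundation paragraph under RESEARCH ENVIRONMENT restricts access to patient data to one group of study staff in investigator and coordinator roles. It does not say which of them processes the tagged images.
- **Tool.** The opening of DATA ANALYSIS has tagged images processed "using the HARP® tagging analysis software package (Diagnosoft) or a similar industry standard software package". That sentence mentions neither PET class nor cohort.
- **Quality loss.** The Powering Calculation says "We anticipate approximately 15% of patients that may not achieve sufficient quality of data". It gives no criterion, assessor or timing.

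The text supplied contains no statement on masking, coded images, repeat reading or a data lock before PET labels are attached.

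**The concern.** In both primary end-points the PET label is the comparison factor: End-Point 1 compares cohorts and End-Point 2 compares segment classes. The hypothesis tells a reader what to expect, namely that mechanics change with ischemic or fibrotic burden. If any choice made during tag processing, or any decision that data are unusable, is influenced by knowing the label, the influence falls on the contrast being tested. The planned ANOVA and t-tests cannot separate it from a true difference, and a larger sample would only estimate the biased difference more precisely.

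Followed literally, the text has labels assigned before measurement and measurement organised by label. Nothing elsewhere in the text supplied prevents that.

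**Working it through.** **1. The texts side by side.**

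| Question | What the plan gives |
|---|---|
| When are segments labelled? | From PET, in the sentence before strain is calculated |
| When is cohort known? | Before participation, from the qualifying PET study |
| Who reads the tags? | Not stated; access to data limited to one staff group |
| Is the reader masked? | Not stated |
| Rule for rejecting data? | Not stated; about 15% of patients expected to be lost |

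A route from label to measurement is therefore open. The documents do not show that it is used.

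**2. The plan's own sample size.** Inputs from the Powering Calculation: d = 1.06 (5.6/5.3 = 1.06), power 0.8, 16 per group or 13 versus 22 evaluable, 15 and 25 enrolled. Alpha is not stated; I assume two-sided 0.05. With the noncentral t distribution:

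- 15 per group gives power 0.800 and 16 per group gives 0.827, so the stated 16 is reproduced to within one patient.
- For 13 versus 22, the noncentrality is 1.06 × √(13 × 22/35) = 1.06 × 2.859 = 3.03 on 33 degrees of freedom, and power is 0.837.

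The stated size is adequate on its own terms, and this point does not change it.

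**3. Illustration for End-Point 1: a reading shift.** Suppose there is no true difference, but label-driven reading moves one cohort by b SD. The false-positive rate is P(|T| > 2.035), where T is noncentral t with 33 degrees of freedom and noncentrality 2.859 × b.

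| Assumed shift b (SD) | Noncentrality | False-positive rate |
|---|---|---|
| 0 | 0 | 5.0% |
| 0.1 | 0.29 | 5.9% |
| 0.2 | 0.57 | 8.6% |
| 0.3 | 0.86 | 13.2% |
| 0.4 | 1.14 | 19.9% |
| 0.5 | 1.43 | 28.4% |

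No document gives a value for b. The shifts should not be read as fractions of d = 1.06 either, because that d rests on the SD of resting LVEF (5.3%), not on an SD of strain or rotation.

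**4. Illustration for End-Point 1: label-dependent rejection.** The planned losses are 15 − 13 = 2 and 25 − 22 = 3. In a simulation with no true difference (40,000 runs), random losses leave the false-positive rate at 5.1%. If each loss has a 50% chance of being the patient least in line with the hypothesis, the rate is 14.4%. If every loss is such a patient, it is 33.4%, the worst case. These probabilities are also assumptions.

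**5. End-Point 2.** Both illustrations count patients in two cohorts. End-Point 2 compares segments by class, and the plan gives no sample size for it, so no corresponding figure can be calculated.

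**The case against.** A reader might infer that the plan prescribes labelled reading and so builds in a bias. The documents do not support that.

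- **The order is ambiguous.** DATA ANALYSIS describes tag post-processing first, without reference to PET class. A value per segment category cannot be tabulated until categories exist, so *then* may describe grouping of results as well as reading order. This stands. Even so, the grouping reading does not assure unlabelled processing.
- **The reader is not identified.** Manual contouring, frame selection, and one person holding both the labels and the tags are inferences. The access rule makes overlap possible but does not show it. This stands.
- **The 15% is a planning allowance for patients.** Some losses may arise at acquisition, before any processing, and coded reading would not affect those. This stands, but the plan still has no criterion for calling data unusable.
- **Part of a reading tendency may cancel.** The plan allows the measure to be a difference between stress and rest. A shift equal at both would drop out, leaving only a shift specific to one state. This stands for the difference measure, but not where rest and stress values are compared as such.
- **The review copy is incomplete.** Some text was removed before review, so absence of masking is established only for the text supplied.

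**Conclusion.** The point holds as a missing safeguard. PET labels precede the MRI, the written sequence puts labels before strain, both primary end-points compare PET-defined categories, and no supplied text masks the reader or sets a rejection rule. It does not hold as a demonstrated bias, because the documents show neither who reads the images nor that the reader knows the labels.

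The size is unknown. The illustrative range, about 9% to 20% false positives instead of 5%, applies to End-Point 1 only. It rests on an assumed shift of 0.2 to 0.4 SD, 13 versus 22 evaluable patients and an assumed two-sided 0.05 test. The recommendation is worth adopting because it is cheap and protects both primary comparisons, not because any particular inflation has been established.

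**What to change.** Add to the Primary End-Point Analysis that:

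1. Rest and stress tagged images are processed under a study code, without PET report, cohort or segment class. An existing staff member who does not read the tags holds the key.
2. Usable or unusable decisions are made at that step against criteria set in advance, and recorded.
3. The segment-level file of strain and rotation is locked before PET classes and cohort are merged into it.
4. Exclusions are reported by cohort and by segment class.

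This needs no extra patient, scan or reader, and leaves the sample size unchanged. The cost is a short addition to the text, quality criteria written in advance, and the coding of about 40 studies. One limit remains: if the reader also took part in selecting patients from PET, masking may be partial, and the report should say so.

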Cardiac magnetic resonance (CMR) imaging is increasingly being used in the assessment of regional and global left ventricular function at rest and during vasodilator stress (16-18). CMR has many important technical advantages including a higher spatial resolution than PET or SPECT, improved tissue characterization (both with and without contrast), and superior repeatability and endocardial definition (including functional assessment) over echocardiography. Its power of tissue characterization is particularly highlighted with the use of late gadolinium enhancement (LGE) and its excellent spatial correlation with infarction, necrosis, and fibrosis (19). With respect to wall motion, myocardial strain imaging with CMR uses magnetic saturation "tag" lines (figure 1) to aid in qualifying and quantifying wall motion, is superior to echo-based strain techniques, and has been demonstrated to correlate well with LVEF (20-23).

At this time, there is ample evidence that vasodilator stress induces functional changes (4-7,9,11,12); however, without an understanding of the etiology of this process, its value in patient management is limited. In order to use functional changes induced by vasodilator stress, it is necessary to first understand the relationship between functional and perfusion abnormalities, local strain and fibrotic burden.

It is the intent of this research to quantify the effects of regadenoson on myocardial function and contraction in the presence of CAD. We are proposing a CMR protocol to evaluate myocardial viability and function, with CMR tagging, on a segment-based approach. We plan to evaluate correlations in wall motion changes (ie. - myocardial radial strain (ΔR) and/or displacement ($\Delta\theta$)) during regadenoson stress and correlate with areas of myocardial infarction (late gadolinium enhancement on CMR), areas with identified perfusion defect (on PET), and a change in LVEF magnitude (on both PET and CMR).

Figure 1: Tagged short axis cine view of the left ventricle (left panel) and late gadolinium enhancement image (right panel) showing a near transmural infarction of the septal wall.

HYPOTHESIS

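### The primary analysis names no unit of analysis, pairing or patient term for segment-level strain and rotation, so it does not exclude tests that treat correlated segments of one patient as independent

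*Combined protocol and SAP*

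**What the plan says.** - **Classification (DATA ANALYSIS, Primary End-Point Analysis).** "every segment of the myocardium will be classified as normal, reversible, or non-reversible based on the PET perfusion data". The next sentence begins "Then for each segment category the radial strain" and adds rotation, from three short-axis views at stress and rest. It does not say whether values are averaged within a patient or pooled over patients.
- **Method (same section).** "Comparisons will be made using ANOVA and standard t-test methods". Nothing on the unit, pairing, repeated measures or clustering is added there or elsewhere in the text available.
- **End-Point 1 (PRIMARY END-POINTS).** The comparison is "of normal and abnormal segments between the defined ischemic and normal patient groups".
- **End-Point 2.** PRIMARY END-POINTS compares "between segment classifications (normal, reversible, and non-reversible perfusion defects", which is three classes. DATA ANALYSIS compares "between abnormal and normal segment classifications", which is two.
- **Hints about the unit.** The background states: "We are proposing a CMR protocol to evaluate myocardial viability and function, with CMR tagging, on a segment-based approach". The Powering Calculation, by contrast, counts patients: d = 1.06, with 13 normal and 22 abnormal patients for power 0.8.
- **Cohorts (STUDY PROCEDURES).** Ischemic patients are those "with a clinically indicated myocardial perfusion PET study demonstrating reversible ischemic perfusion defect". The normal cohort has normal perfusion, so it should supply normal segments only.

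**The concern.** Segments of one heart share that patient's loading, heart rate, image quality and drug response, so they may well be positively correlated. A standard t-test or one-way ANOVA on segments ignores this. In End-Point 1 every segment of a patient falls on the same side of the comparison, so ignoring positive correlation makes the standard error too small.

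End-Point 2 is different because abnormal and normal segments can come from the same patient. Ignoring the pairing can push the error either way, and a two-sample test on class means from the same patients wastes power.

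The validity of both primary end-points therefore depends on a choice left open until the data are in hand. The regressions under Secondary End-Point 1 have the same problem if run on segments.

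**Working it through.** **1. The plan's own figure.** From the Powering Calculation, d = 5.6 / 5.3 = 1.06. The documents give no alpha; two-sided 0.05 is assumed throughout. The normal approximation gives 2 × (1.96 + 0.8416)² / 1.06² = 13.97, so 14 per group. The t-test needs 15, and a rank-test variant 16, which is the stated number. At 13 vs 22 the noncentrality is 1.06 × √(13 × 22 / 35) = 3.03 and the t-test power is 0.84. The stated sizes are reproduced closely, with the patient as the unit.

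**2. End-Point 1 with segments taken as independent.** Not in the documents, and assumed: m segments per patient (6 or 16), the ICC, and no slice-level mean differences. The design effect is DE = 1 + (m − 1) × ICC, and the actual type I error is about 2 × [1 − Φ(1.96 / √DE)].

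| m | ICC | DE | Formula | Simulated |
|---|---|---|---|---|
| 6 | 0.05 | 1.25 | 0.080 | 0.078 |
| 6 | 0.1 | 1.50 | 0.110 | 0.108 |
| 6 | 0.5 | 3.50 | 0.295 | 0.300 |
| 16 | 0.05 | 1.75 | 0.138 | 0.137 |
| 16 | 0.1 | 2.50 | 0.215 | 0.213 |
| 16 | 0.5 | 8.50 | 0.501 | 0.503 |

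The simulation used 20,000 null trials per cell, 13 vs 22 patients, comparing all segments. By class, with 16 segments of which 5 are abnormal, error runs over ICC 0.02 to 0.5 from 0.079 to 0.470 (normal segments of ischemic patients vs controls) and from 0.070 to 0.378 (abnormal vs controls). Welch tests on patient means stay at 0.045 to 0.052.

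**3. Effect of slice-level differences.** Suppose apical, mid and basal means differ by −1 / 0 / +1 SD and slice is ignored. The naive residual variance grows and can hide the clustering. At ICC 0.05:

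- 16 segments (assumed 4 / 6 / 6): slice variance 0.609; true variance of a patient mean 0.05 + 0.95/16 = 0.109; naive variance 1.609/16 = 0.101; ratio 1.087; error about 0.060 (simulated 0.058 to 0.061).
- 6 segments (2 / 2 / 2): slice variance 0.667; true 0.05 + 0.95/6 = 0.208; naive 1.667/6 = 0.278; ratio 0.75; error about 0.024 (simulated 0.022 to 0.029).

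Inflation therefore requires positive correlation in the data as pooled, after such differences have entered the residual.

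**4. End-Point 2, unpaired on segments.** Simulated null rejection with 16 segments:

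| Setting | ICC 0.02 | ICC 0.5 |
|---|---|---|
| 5 abnormal in every ischemic patient | 0.049 | 0.008 |
| Abnormal count varies 1 to 12 | 0.051 | 0.166 |
| Controls pooled in | 0.053 | 0.130 |
| Both | 0.062 | 0.285 |
| 5 abnormal; class effect varies between patients (SD 0.5) | 0.132 | 0.087 |

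With 6 segments the first four settings range from 0.007 to 0.107. The paired test on class means holds 0.046 to 0.053.

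**5. End-Point 2, two-sample test on class means of the same 22 patients.** Take 5 abnormal of 16, ICC 0.1 and a difference of 0.2 SD. The correct variance is (0.9/11 + 0.9/5)/22 = 0.0119, SE 0.109. The two-sample test uses (0.1 + 0.9/11 + 0.1 + 0.9/5)/22 = 0.0210, SE 0.145. Its simulated null rejection is 0.011, and its power is 0.21 against 0.42 for the paired test. With 2 abnormal of 6 segments at the same ICC the loss is smaller: 0.135 against 0.193.

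**6. Multiplicity at patient level.** Two unadjusted Welch tests for End-Point 1 give at least one false positive in about 0.07 to 0.09 of trials. Three unadjusted paired class comparisons for End-Point 2 give about 0.12; with Holm, 0.041 to 0.044.

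**The case against.** The strongest reply is that the plan already points to the patient: its sizing counts patients, and calculating strain by segment category can be read as one value per patient and class. That reading is open and, with pairing for End-Point 2, valid. A reader might infer that the plan prescribes a segment-level analysis. It does not; the segment-based phrase in the background describes how the heart is evaluated, not the statistical unit. What remains is that nothing in the analysis section tells an analyst to average or pair.

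A second objection concerns size. The documents give no segment count, ICC or alpha, and step 3 shows that slice differences can offset the inflation at low ICC. This stands: the figures are assumed ranges, and the direction for End-Point 1 is conditional.

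A third is that a mixed model is no automatic cure. This also stands. If rest and stress are both entered with only patient, class-by-patient and segment effects, all of these cancel in the stress-minus-rest contrast, and segment changes are again treated as independent. With 16 segments the error is then 0.14 / 0.21 / 0.51 when changes correlate 0.05 / 0.1 / 0.5 within patient.

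**Conclusion.** The omission is real and should be fixed. The stated method, applied to segments, gives wrong standard errors, and the plan does not rule that out.

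- **End-Point 1.** Type I error exceeds nominal when segments of one patient are positively correlated in the pooled data. Under the step 2 assumptions it is about 0.13 to 0.50 with 16 segments and 0.08 to 0.30 with 6, over ICC 0.05 to 0.5.
- **End-Point 2.** A reader might infer inflation here too. No single direction holds: it depends on how abnormal counts vary, whether controls are pooled in, and whether the class effect varies between patients. The two-sample test on class means is conservative and loses power, by an amount that depends on effect size, segment count and ICC.
- **Sample size.** A reader might also infer that the sample size is wrong on this account. It is not: it is patient-based and reproduces. But d = 1.06 comes from LVEF and an assumed geometry, so 0.84 is not the power of the class-specific strain or rotation contrasts, for which the documents give no variance.

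**What to change.** In the Primary End-Point Analysis, state that the patient is the independent unit and that strain and rotation are averaged per patient and segment class. Then:

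- **Measure and state.** Name one measure (strain or rotation) and one state (rest, stress, or stress minus rest) as primary, or adjust across them.
- **End-Point 1.** Welch tests on patient means of (a) normal and (b) abnormal segments of ischemic patients, each against control segments, with Holm adjustment or one named as primary.
- **End-Point 2.** Paired tests within ischemic patients on the three classes in PRIMARY END-POINTS, with Holm adjustment. Reversible vs normal is the natural lead, since these patients are selected for a reversible defect. Make PRIMARY END-POINTS and DATA ANALYSIS agree on the classes.
- **Alternative.** A linear mixed model on segments with slice level is acceptable only if a single state or the stress-minus-rest difference is the outcome, or if patient-by-state and class-by-patient-by-state random effects are included.
- **Secondary regressions.** Use a patient random effect, or patient-clustered errors with a small-sample correction.
- **Reporting.** State alpha and the number of segments per patient, and report the ICC.

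The cost is a short rewrite of the analysis section, with no new data. End-Point 1 p-values will usually be less favourable than in a segment-level analysis. Patients lacking a class drop out of that paired contrast, which may leave few for the non-reversible comparisons.

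### Primary End-Point 2 is defined over three segment classes, but its analysis item compares only abnormal with normal segments, leaving reversible versus non-reversible unassigned

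*Combined protocol and SAP*

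**What the plan says.** Under PRIMARY END-POINTS, Primary End-Point 2 looks for measurable differences in strain and/or displacement "between segment classifications (normal, reversible, and non-reversible perfusion defects"). The HYPOTHESIS section has the same three-way structure: "these changes may be different for normal, ischemic, and infarcted myocardium".

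Under DATA ANALYSIS, Primary End-Point Analysis, the lead-in paragraph states that "every segment of the myocardium will be classified as normal, reversible, or non-reversible based on the PET perfusion data". It has strain and displacement calculated for each category and adds: "Comparisons will be made using ANOVA and standard t-test methods". Two numbered items follow, one per endpoint. Item 2, for Primary End-Point 2, compares strain and displacement at rest and stress "between abnormal and normal segment classifications".

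The plan does not define *abnormal* for a segment, and it does not say whether the reversible and non-reversible classes are to be combined.

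**The concern.** The endpoint has three levels and the sentence assigned to it has two. Two analysts could follow this plan in good faith and run different primary analyses: one pooling the abnormal segments against normal, the other comparing three classes. Only the second covers the endpoint as written. The distinction that would be lost, between reversible and non-reversible defects, is the one closest to the ischemic-versus-infarcted part of the hypothesis. If the choice stays open, it could be made after the data have been seen.

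**Working it through.** The claim is about wording, so the main check sets the texts side by side.

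| Place | Levels of segment class |
|---|---|
| HYPOTHESIS | three tissue types |
| PRIMARY END-POINTS, End-Point 2 | three PET classes |
| Primary End-Point Analysis, lead-in | three PET classes |
| Primary End-Point Analysis, item 2 | abnormal and normal |

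**Is item 2 just consistent shorthand?** For End-Point 1, both the definition and analysis item 1 speak of normal and abnormal segments, so the two agree. For End-Point 2 the definition lists three classes and the item does not. The mismatch is specific to End-Point 2.

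**Does another section supply the missing contrast?**

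- *Methods sentence.* ANOVA and t-tests are named for both endpoints together; neither method is assigned to one endpoint. An omnibus three-class ANOVA would be allowed, but would not by itself show which classes differ.
- *Secondary End-Point 1.* This is a regression involving flow reserve and transmural extent of infarction from late enhancement. It is not a comparison of PET classes, and subjects on the non-contrast protocol have no late-enhancement data.
- *Powering Calculation.* The effect size reproduces as 5.6 / 5.3 = 1.06. With two-sided alpha 0.05 (assumed, since the plan states none), a two-sample t-test at 80% power needs 15 per group, against the plan's 16. Power "using an unequal population sizes of 13 (normal) and 22 (abnormal") is 0.84, against the stated 0.8. The calculation compares patient groups, so it does not say how segment classes are to be handled.

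**Why a pooled contrast cannot stand in.** Let R and N be the mean differences from normal for reversible and non-reversible segments, and p the non-reversible share of abnormal segments. The pooled difference is pN + (1 − p)R. Illustration in arbitrary units with p = 0.2:

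- N = 1, R = 0.5: 0.2 × 1 + 0.8 × 0.5 = 0.6
- N = 0.6, R = 0.6: 0.2 × 0.6 + 0.8 × 0.6 = 0.6

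The pooled result is the same, yet N − R is 0.5 in the first case and 0 in the second. Pooling cannot tell them apart.

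**Who can supply reversible versus non-reversible.** Only the ischemic cohort, because in the other cohort "15 subjects will be recruited who had normal perfusion, normal LVEF and no WMA". The plan does not say how many ischemic subjects will have both abnormal classes. Purely as an illustration, take patient-level class means and one within-patient difference per subject. The 95% half-width in SD of that difference is t(0.975, n − 1)/√n:

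| Subjects with both classes (assumed) | Half-width |
|---|---|
| 22 (every subject in the planned evaluable ischemic group) | 0.44 |
| 11 | 0.67 |
| 6 | 1.05 |

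These figures show the precision the fix might buy. They do not measure the defect.

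**The case against.** The strongest reply is that the lead-in sits under the same heading and governs item 2. It sets up three classes, has values calculated for each, and names a method suited to more than two groups. Item 2 then refers to segment classifications, the phrase that the endpoint definition expands into three classes. On that reading *abnormal* is an umbrella term and nothing is missing.

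Much of this stands. A reader might infer that the plan has no three-class analysis at all, or that it has decided to pool; the documents support neither inference. The lead-in permits a three-class analysis, and no sentence says that the classes are combined. What the reply does not do is remove the ambiguity. Even if item 2 is taken to mean each abnormal class against normal, reversible versus non-reversible is still left out.

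It is also fair to say that the endpoint does not demand a fixed set of pairwise tests. It says and/or for the two measures, the endpoint text allows a stress–rest difference in place of separate states, and an omnibus test would address it in part. A reader might infer a definite number of omitted comparisons; any such count rests on one reading among several.

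**Conclusion.** The point holds as a conflict between a primary endpoint and the analysis sentence assigned to it. Of the three contrasts that three classes allow, reversible versus non-reversible is named nowhere in the analysis section, and an analyst following item 2 literally would not estimate it. If the abnormal classes are pooled, End-Point 2 as defined goes unanswered.

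The conclusion rests on the text alone and needs no numerical assumption. A reader might go further and infer a biased result, lost power or a wrong sample size. The documents do not support that: the sizing concerns patient groups and is unaffected, and the number of subjects with both abnormal classes is not given, so no loss can be calculated. The plan should be corrected before analysis, and the correction is cheap.

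**What to change.** Reword item 2 to compare strain and displacement across the three PET classes already assigned to every segment, naming reversible versus non-reversible explicitly alongside each abnormal class versus normal. Because each patient contributes several segments, use a model that allows for this, such as a random patient effect or patient-level class means, in place of ANOVA or t-tests that would treat segments as independent. Since several contrasts are then named, state whether and how multiplicity is handled.

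If the sponsor means to pool the two abnormal classes, the consistent alternative is to say so in item 2 and amend Primary End-Point 2 to a two-class comparison.

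Either route is a short text change and needs no new data. The cost of the three-class route is precision. The ischemic cohort is chosen from PET studies "demonstrating reversible ischemic perfusion defect", so the non-reversible class may be small. Its contrast may have to be reported mainly as an estimate with a wide interval, and any multiplicity rule takes some further power.
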